9.7 Definition of On-treatment Period

On-treatment period is defined as the time from the first trial drug administration to the last trial drug administration date + 30 days OR the earliest date of subsequent anti-cancer therapy (including drugs, surgeries, radiotherapies) minus 1 day, whichever occurs first, unless otherwise stated.

For immune-related AEs as listed in Section 16.1.3.2, an expanded on-treatment period will be used as a default for any analysis:

Time from the first study intervention to the last study intervention date + 90 days, death OR to the earliest date of subsequent anticancer therapy minus 1 day, whichever occurs first, unless otherwise stated.

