6.5.1 Permitted Medicines

Any medications (other than those excluded by the clinical trial protocol) that are considered necessary to protect subject welfare and will not interfere with the trial medication may be given at the Investigator's discretion.

Other drugs to be used for prophylaxis, treatment of anaphylactic reactions, infusion-related reactions, and severe hypersensitivity reactions/flu-like symptoms and irAEs are described in Sections 5.1.7.2, 6.4, and 6.5.4.

Palliative bone directed radiotherapy may be administered during the trial. The assessment of PD will be made according to RECIST 1.1 (Eisenhauer 2009) and not based on the necessity for palliative bone-directed radiotherapy.

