8.5.5.1 Adverse Events

Adverse events will be coded according to the most current version of MedDRA. Severity of AEs will be graded using the NCI-CTCAE v4.03 toxicity grading scale.

The incidence TEAEs regardless of attribution and AEs defined as related to MSB0011359C will be summarized by Preferred Term and System Organ Class, and described in terms of intensity and relationship to MSB0011359C. Adverse events (serious and nonserious) will be considered TEAEs when emerging in the on-treatment period defined as the time from the first trial drug administration to the last drug administration date + 30 days or the earliest date of subsequent anticancer drug therapy minus 1 day, whichever occurs first, unless otherwise stated. AEs occurring after the last trial drug administration will always be classified as TEAE if it is considered trial drug-related by the Investigator. All premature terminations will be summarized by primary reason for treatment withdrawal.

1

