6.1 Decision after discontinuation of NSCLC and BTC trials

The data review outcome from the 3 randomized controlled studies in NSCLC and BTC (MS200647-0005, MS200647-0037, MS200647_0055) appears to indicate, consistently across 2 indications, either poorer observed hazard ratios for PFS and OS in the experimental arms with bintrafusp alfa or low likelihood for bintrafusp alfa to add benefits compared to standard of care. Based on this, the decision was made to not perform any final analysis after the final database lock. The study results have been described in the CSR approved on 31 March 2020 (cut-off date: 24th August 2018) and on CSR addendum approved on 25 March 2021 (cut-off date: 15th May 2020).

7 Changes to the Planned Analyses in the Clinical Study Protocol

There will be no final analysis after the final database lock.

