12.1 Previous and concomitant medications

Pre-ICF medications are medications, other than study medications, which were taken within 30 days prior to signing the informed consent and were stopped prior to the signing of the informed consent.

Previous medications are medications, other than study medications and pre-medications for study drug, which are started before first dose date of study treatment. Pre-ICF medications which continue past the time of signing the informed consent will be categorized as previous medications. In case the date values will not allow to unequivocally allocate a medication to previous medication the medication will be considered as previous medication.

Concomitant medications are medications, other than study medications and pre-medications for study drug, which are taken by participants any time on-trial (on or after the first day of trial drug treatment for each participant) or within 30 days after last dose of trial drug OR the earliest date of subsequent anti-cancer drug therapies minus 1 day, whichever occurs first. In case the date values will not allow to unequivocally allocate a medication to concomitant medication the medication will be considered as concomitant medication.

Post follow-up medications are medications, other than study medications and pre-medications for study drug, which are started on or 30 days after last dose of trial drug OR on or after the earliest date of subsequent anti-cancer drug therapies, whichever occurs first.

Previous and Concomitant treatments will be summarized separately from the "Concomitant Medications Details" eCRF page. These summaries will present the number and percentage of participants by drug class and preferred term, overall and by dose level/cohort. Drug class will be derived as ATC classification Level 2, and the preferred term will be taken as the preferred drug name, based on the most recent available version of the WHO-DD dictionary. If multiple ATCs are assigned to a drug, all ATCs for that drug will be reported. A participant will be counted only once within a given drug class and within a given drug name, even if he/she received the same medication at different times. The summary will be sorted by ATC-2nd Level and Preferred Term in alphabetical order.

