16.1 Adverse Events

Treatment emergent adverse events (TEAEs) are those events with onset dates occurring during the on-treatment period for the first time, or if the worsening of an event is during the on-treatment period as defined in Section 9.7. Adverse events will be coded according to the most current version of MedDRA. Severity of AEs will be graded using the NCI-CTCAE v4.03 toxicity grading scale.

Changes in toxicity grade, seriousness or outcome of AEs are recorded as separate entries in the eCRF with associated end and start dates (start date equals end date of previous entry). Such entries reporting the same event in such immediately consecutive periods will be considered as one event in the analysis in case of a change in toxicity grade. These events will be kept as separate records in the database in order to maintain the full detailed history of the events. The start date of the initial record in the sequence is taken as start date of the entire event. Duration of the AE and the TEAE flag will be adjusted accordingly in the analysis.

All analyses described in this section will be based on TEAEs if not otherwise specified. The AE listings will include all AEs (whether treatment-emergent or not).

- **Related Adverse Events**: adverse events with relationship to study treatment (as recorded on the "Adverse Events Details" eCRF page, Relationship with MSB0011359C= Related) reported by the investigator and those of unknown relationship (i.e. no answer to the question "Relationship with MSB0011359C").
- **Serious Adverse Events (SAE)**: serious adverse events (as recorded on the "Adverse Events Details" eCRF page, Serious Adverse Event = Yes).
- Adverse Events leading to Treatment Discontinuation: adverse events leading to permanent discontinuation of study treatment (as recorded on the "Adverse Events Details" eCRF page, Action taken with MSB0011359C = Drug withdrawn).
- Adverse Events leading to Death: adverse event leading to death (as recorded on the "Adverse Events Details" eCRF page, Outcome = Fatal, as well as AEs of Grade 5).
- Adverse Events of Special Interest (AESI): adverse events of special interest (as identified according to a pre-specified search list of MedDRA Preferred Terms). Categories of AESI include:

- o Immune-Related Adverse Events (irAE)
- o Infusion-Related Reactions (IRR) including hypersensitivity
- O Skin AE possibly related to TGFβ inhibition
- o Anemia

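### SAP 9.7 closes the on-treatment period at post-discontinuation surgery or radiotherapy as well as drug therapy; protocol 8.5.5.1 closes it at drug therapy only, and the change is not declared

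*SAP*

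**What the plan says.** - **SAP 9.7** runs the on-treatment period from the first dose to the last dose plus 30 days, or to "the earliest date of subsequent anti-cancer therapy (including drugs, surgeries, radiotherapies) minus 1 day, whichever occurs first".
- **Protocol 8.5.5.1** has the same start and the same 30-day limit, but the other stopping point is "the earliest date of subsequent anticancer drug therapy minus 1 day, whichever occurs first". It adds a safeguard: "AEs occurring after the last trial drug administration will always be classified as TEAE if it is considered trial drug-related by the Investigator".
- **SAP 16.1** counts as treatment-emergent "those events with onset dates occurring during the on-treatment period for the first time", or events that worsen in that period as 9.7 defines it. It does not repeat the protocol's safeguard for related events.
- **SAP 12.4** collects later treatment from the drug, radiotherapy and surgery pages. It uses the first such treatment after discontinuation for two purposes: the on-treatment period and efficacy censoring. Palliative treatment is not exempted.
- **SAP 12.1** closes the concomitant-medication window 30 days after the last dose or at "the earliest date of subsequent anti-cancer drug therapies minus 1 day, whichever occurs first".
- **SAP Section 7**, on changes to the protocol's analyses, says only "There will be no final analysis after the final database lock", apart from the COVID-19 outputs in 7.1.
- **The 90-day window for immune-related AEs** (SAP 9.7 and 16.2.3.2) stops at death or later anticancer therapy. It does not list surgery or radiotherapy.

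**The concern.** Safety and tolerability are the primary objective (protocol 4.1). The number, severity and duration of TEAEs are among the primary endpoints of the dose escalation part (protocol 8.3.1). Which therapies close the window is therefore part of a primary-endpoint definition, and the SAP has narrowed that definition without saying so.

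The SAP also disagrees with itself: AEs and concomitant medications in the same report would be cut by different rules. A participant who has radiotherapy a week after the last dose, with no new drug, would stay in the concomitant-medication window but leave the AE window.

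At stake are the TEAE, serious-TEAE and fatal-TEAE tables, and the laboratory, ECG and vital-sign change summaries that SAP 16.4 to 16.6 limit to the on-treatment period.

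**Working it through.** There is no stated figure to reproduce and no test is involved. The check sets the two definitions side by side and counts days.

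**Inputs**
- The 30-day limit is in both documents.
- d is the day after the last dose on which local anticancer therapy (surgery or radiotherapy) starts, following discontinuation.
- s is the day on which the first later anticancer drug starts.
- The documents give no values for d or s, so those below are assumed and span the range.

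**Formulas**
- End of period, protocol: min(30, s − 1)
- End of period, SAP: min(30, s − 1, d − 1)
- Days lost: protocol end minus SAP end. With no drug by day 30 and d ≤ 30, this is 30 − (d − 1) = 31 − d.

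| Local therapy on day d | No drug by day 30: protocol end, SAP end, days lost | Drug on day s = 21: protocol end, SAP end, days lost |
|---|---|---|
| 1 | 30, 0, **30** | 20, 0, **20** |
| 7 | 30, 6, **24** | 20, 6, **14** |
| 14 | 30, 13, **17** | 20, 13, **7** |
| 21 | 30, 20, **10** | 20, 20, **0** |
| 28 | 30, 27, **3** | 20, 20, **0** |
| 31 or later | 30, 30, **0** | 20, 20, **0** |

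**Direction.** The SAP end is the minimum of the protocol's terms and one more, so it can never be later than the protocol end. Every event inside the SAP window is also inside the protocol window. Counts of participants with a TEAE, a serious TEAE or a fatal TEAE can only stay equal or fall. The same holds for the worst on-treatment value or grade reached.

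**Related and unrelated events.** Under protocol 8.5.5.1, an event after the last dose that the investigator considers related stays a TEAE whatever closes the window. If that rule is in force, the wider trigger removes mainly events judged unrelated. Related events are lost as well only because SAP 16.1 leaves the rule out. That is a second departure, which the trigger exposes but does not cause.

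**What is not touched**
- Deaths are tabulated within 30 days of the last dose and 60 days of the first dose, with no cut at later therapy (SAP 16.2.1).
- Infusion-related reactions are tied to the day of infusion or the day after (SAP 16.2.3.1).
- The AE listings keep all events (SAP 16.1).
- Related serious AEs keep a category 3 narrative after the period ends (SAP 16.3).
- An AE that leads to discontinuation normally starts before any post-discontinuation therapy, so those tables barely move.

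**The case against.** **The protocol leaves room for this.** Its definition ends with a let-out: "the earliest date of subsequent anticancer drug therapy minus 1 day, whichever occurs first, unless otherwise stated". Section 8.5.5.3 also leaves further safety-analysis detail to the SAP. Closing the window at local therapy keeps out events caused by the operation or the radiation, which is a defensible choice. This stands as an argument for the wider rule. It does not excuse leaving the rule undeclared in the section meant for such changes, or using a different rule in SAP 12.1.

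**Days lost are not events lost.** The End-of-Treatment visit is due at 28 ± 5 days and, if possible, before any new therapy (protocol 7.1.4.2). After it, only events attributed to trial drug are recorded (7.4.1.3). If the visit is brought forward, some unrelated events in the lost days may never be collected. This stands: 31 − d is an upper limit on time, not an event count.

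**Stronger readings a reader might infer, which the documents do not support:**
- *That palliative radiotherapy during treatment closes the window.* The protocol states "Palliative bone directed radiotherapy may be administered during the trial", and SAP 12.4 counts only therapy after discontinuation. SAP 9.7 does not say this itself, so the answer rests on reading the two sections together.
- *That all on-treatment safety tables lose these events, or that fatal events vanish.* The outputs listed as untouched in the working show otherwise. A fatal event judged unrelated could lose its category 1 narrative, but it stays in the death listing.
- *That the 90-day immune-related window shrinks in the same way.* Its wording omits surgery and radiotherapy, and protocol 8.5.5.1 has no such window to contradict. The wording is ambiguous; a loss is not shown.
- *That the affected participants are the sickest, so that toxicity is understated by a known amount.* Nothing in the documents gives their number or condition.

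**Conclusion.** The point holds as an undeclared and internally inconsistent narrowing of the TEAE definition. It does not hold as a general loss of safety data.

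The loss is 0 to 30 days of follow-up per affected participant, and none if local therapy starts on day 31 or later. The direction is certain: the affected counts cannot rise. The number of participants and events cannot be derived from the documents.

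This assumes that SAP 12.4 limits the trigger to therapy after discontinuation. The contribution from related events depends on whether the omission in SAP 16.1 was intended.

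The CSR and its addendum are already approved (SAP 6.1). The point still matters because SAP Section 4 allows these analyses to be used in regulatory submissions and manuscripts.

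**What to change.** 1. In SAP 9.7, replace "the earliest date of subsequent anti-cancer therapy (including drugs, surgeries, radiotherapies) minus 1 day, whichever occurs first" with the protocol's trigger, "the earliest date of subsequent anticancer drug therapy minus 1 day, whichever occurs first".
2. In SAP 12.4, make the same change for the on-treatment period only. That sentence also governs efficacy censoring, which this point does not concern.
3. State in SAP 9.7 and 16.2.3.2 which therapies close the 90-day immune-related window.
4. Restore the protocol's rule for related events after the last dose in SAP 16.1, or declare its removal in Section 7.
5. If the wider trigger is kept, declare it in Section 7 and also present the TEAE, serious-TEAE and fatal-TEAE tables under the protocol rule.

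**Cost.** A few wording changes and one re-derived flag. Because the outputs have been delivered, the affected tables would need a rerun. A few events caused by radiotherapy or surgery would be counted as treatment-emergent; the listings would let a reader identify them.

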9.8 Imputation of Missing Data

Incomplete dates (date of informed consent, date of birth) for the calculation of age will be imputed as follows:

- In case of missing day for at least one date, but month and year available for both dates: the day of informed consent and the day of birth will be set to 1.
- In case of missing month for at least one date, but year available for both dates, the day and the month of informed consent and the day and month of birth will be set to 1.

Incomplete AE-related dates will be imputed as follows:

- In case the onset date is missing completely or missing partially but the onset month and year, or the onset year are equal to the start of trial treatment then the onset date will be replaced by the minimum of start of trial treatment and AE resolution date (if not missing).
- In all other cases the missing onset day or missing onset month will be replaced by 1.
- Incomplete stop dates will be replaced by the last day of the month (if day is missing only), if not resulting in a date later than the date of participant's death or cutoff date. In the latter case the date of death or cutoff date will be used to impute the incomplete stop date.
- In all other cases the incomplete stop date will not be imputed.

Incomplete dates for previous, concomitant and subsequent medications will be imputed as

follows:

- For start date of medication
 - o If the day is missing, it will be imputed to the 1st day of the month.
 - If both day and month are missing, the month and day will be imputed as January
 1st
 - o If the date is completely missing, no imputation will be performed.
- For end date of previous, concomitant and subsequent medications
 - o If the day is missing, it will be imputed to the last day of the month.
 - o If both day and month are missing, the month and day will be imputed as December 31st
 - o If the date is completely missing, no imputation will be performed.

Note: In case the imputation results in a date later than the date of patient's death, then the date of death will be used to impute the incomplete stop date.

Missing or partial death dates will be imputed based on the last known date to be alive (refer to Section 14.4)

- If the date is missing it will be imputed as day after the last known date to be alive
- If the day or month is missing, death will be imputed as the maximum between the last known date to be alive and the imputed date of death where:
 - Missing day: 1st day of the month and year of death
 - Missing day and month: January 1st of the year of death

Missing or partial tumor assessments dates will be imputed based as follow:

- If there are multiple scan dates associated with an evaluation, the earliest of the scan dates associated with the evaluation will be used as the date of assessment.
- If one or more investigation dates for an evaluation are incomplete but other investigation dates are available, the incomplete date(s) are not considered for calculation of the assessment date and assessment date is calculated as the earliest of all investigation dates (e.g. X-ray, CT-scan).
- If all measurement dates for an evaluation have no day recorded, the 1st of the month is used.
- If the month is not completed, for any of the investigations for an evaluation, the respective assessment will be considered to be at the date which is exactly between the previous and the following assessment. If both a previous and following assessments are not available, this assessment will not be used for any calculations.

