12.4 Subsequent Anticancer Therapies

Anti-cancer treatment after discontinuation of bintrafusp alfa will be provided in a data listing with data retrieved from "Anti-Cancer Treatment After Discontinuation Details", "Radiotherapy After Discontinuation Details", and "Surgery After Discontinuation Details" eCRF pages.

The number of participants in each of the following anti-cancer treatment categories will be tabulated, all dose level/cohorts combined (where applicable), and by dose level/cohort:

- Participants with at least one subsequent anti-cancer treatment (i.e. therapy, radiotherapy or surgery)
- Participants with at least one subsequent anti-cancer drug therapy
- Participants with at least one subsequent anti-cancer radiotherapy
- Participants with at least one subsequent anti-cancer surgery

The type of subsequent anti-cancer drug therapy as provided in the e-CRF (i.e. anti-PD-1/anti-PD-L1, cytotoxic therapy, endocrine therapy, monoclonal antibodies therapy, small molecules, immunotherapy except anti-PD-1/anti-PD-L1, other) will be described, as well as the best response across all post trial treatments (complete response, partial response, stable disease, progressive disease, non-complete response/non-progressive disease, not assessable, unknown, not applicable).

In addition, the anti-cancer treatment after discontinuation of bintrafusp alfa will be provided in a data listing including with relevant information.

The earliest date of start of new anti-cancer therapy after discontinuation of bintrafusp alfa will be used for the definition of the on-treatment period and censoring for efficacy analyses

13 Study Treatment: Compliance and Exposure

Analysis set: Safety Analysis Set

The following analyses will be performed based on the safety analysis set by dose level/cohort. All dosing calculations and summaries will be based on "MSB0011359C Administration Details" eCRFs page. A listing of study drug administration will be created with the information collected on the "MSB0011359C Administration Details" eCRF page.

Subjects will receive an IV infusion of bintrafusp alfa over 1 hour (-10 minutes / +20 minutes, that is, over 50 to 80 minutes) once every 2 weeks as detailed in the Schedule of Assessments in the study protocol.

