14.1 Best Overall Response

Best overall response (BOR) will be assessed based on the tumor response at different evaluation time points from baseline until the first documented disease progression. The unconfirmed BOR will be defined by the best overall response reached by the participant during this period, while the confirmed BOR will have to meet additional rules of confirmation as defined in the following sections. Only tumor assessments performed before the start of any further anticancer treatment will be considered in the assessment of BOR. Clinical deterioration will not be considered as documented disease progression.

Objective Response (OR) is defined as complete response (CR) or partial response (PR) according to evaluation criteria from start date until documented disease progression. Patients who do not have an on-treatment radiographic tumor assessment due to early progression, who receive anti-tumor treatments other than the study treatments prior to reaching a CR or PR, or who die, progress, or drop out for any reason prior to reaching a CR or PR will be counted as non-responders in the assessment of OR. Each patient will have an objective response status (0: no OR; 1: OR). OR rate (ORR) is the proportion of patients with OR in the analysis set.

Disease Control Rate (DCR) is defined as the proportion of participants with BOR according to evaluation criteria of CR, PR, or SD. For RECIST 1.1 as adjudicated by IRC, non-CR/non-PD will also be considered in DCR evaluation.

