14.3 Progression-Free Survival

Progression-Free Survival (PFS) time is defined as the time (in weeks) from first administration of trial treatment until the first date of PD or death due to any cause within 84 days (12 weeks) of last tumor assessment if death occurred during the treatment period, or within 168 days (24 weeks) of last tumor assessment if death occurred during the follow-up period.

PFS will be censored in the following scenarios:

- Participants who do not experience an event (PD or death) will be right-censored on the date of the last evaluable (non-missing and non "Not Evaluable") tumor assessment.
- Participants who start new anti-cancer treatment prior to an event will be censored on the date of the last evaluable (non-missing and non "Not Evaluable") tumor assessment before anti-cancer therapy is given.
- Participants with an event after two or more subsequent missing response assessments (i.e. 2 times the scheduled time interval between two subsequent response assessments) will be censored on the date of the last evaluable (non-missing and non "Not Evaluable") tumor assessment.
- Note: 2 times the scheduled time interval means 84 days during the treatment period and 168 days during the follow-up period (for participants who ended the treatment not for progression)
- Participants who do not have a baseline tumor assessment or who do not have any postbaseline tumor assessments will be censored on the date of first dose unless death occurred on or before the time of the second planned tumor assessment in which case the death will be considered an event.

PFS = (date of PD or death/censoring - date of the first dose + 1)/30.4375 (months).

PFS event / censoring are defined in Table 3:

Table 3 Progression-free Survival Event / Censoring

PFS Event Stat	PFS Event Status		Date of event / censoring
Progressed or died Within two subsequent scheduled tumor assessments after last response assessment of CR, PR or SD		Event	Minimum (Date of PD, Date of death)
	Otherwise	Censored	Date of last tumor assessment with outcome CR, PR or SD or date of first dose, whatever is later
Neither progressed nor died		Censored	Date of last tumor assessment with outcome CR, PR or SD or date of first dose, whatever is later

CR = complete response; PD = progressive disease; PFS= progression-free survival; PR = partial response; SD = stable disease.

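### SAP 9.8 gives incomplete start dates of subsequent anticancer therapy no lower bound, so an imputed date can precede the last study dose and wrongly end follow-up windows for those participants

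*SAP*

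**What the plan says.** SAP 9.8 covers three kinds of medication in one rule: "Incomplete dates for previous, concomitant and subsequent medications will be imputed as" set out in its list. For start dates: "If the day is missing, it will be imputed to the 1st day of the month". For year-only dates: "If both day and month are missing, the month and day will be imputed as January" 1st. The only bound in this rule concerns stop dates: if the imputed date would be later than death, "then the date of death will be used to impute the incomplete stop date". By contrast, the death-date rule in the same section has a floor: "death will be imputed as the maximum between the last known date to be alive and the imputed date of death".

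The start of subsequent therapy is then used in several places.

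- SAP 12.4: "The earliest date of start of new anti-cancer therapy after discontinuation of bintrafusp alfa will be used for the definition of the on-treatment" period, and for efficacy censoring. The source is a set of eCRF pages for treatment, radiotherapy and surgery after discontinuation.
- SAP 9.7: the on-treatment period ends at last dose + 30 days or the day before subsequent therapy, whichever is first. The 90-day window for immune-related events is cut in the same way.
- SAP 14.1: "Only tumor assessments performed before the start of any further anticancer treatment will be considered in the assessment of BOR".
- SAP 14.3: "Participants who start new anti-cancer treatment prior to an event will be censored on the date of the last evaluable" scan before that therapy. SAP 14.2 has the same rule for DR.

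**The concern.** Therapy recorded as given after discontinuation cannot have started before the last study dose, but nothing in SAP 9.8 applies that order to an imputed date. The imputed date is never later than the true date, so any error runs one way: windows get shorter and events become censorings. The participants affected have just stopped study treatment, often because of progression, so such censoring would be informative.

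Treatment-emergent AEs are a primary endpoint, and BOR, DR and PFS are secondary. Two expansion cohorts have 30 subjects each, so a single altered record is visible there. SAP section 4 also allows these analyses to be used in regulatory submissions and manuscripts.

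**Working it through.** The documents give no figure to reproduce, so the rule was applied literally to dates and followed through SAP 9.7 and 14.1 to 14.3.

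**Inputs from the documents.** Scans at Week 7 and then every 6 weeks (protocol 7.1.2.2); dosing every 2 weeks; last participant's first dose on 24 August 2017 (SAP section 4); 1 month = 30.4375 days (SAP 9.5).

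**Assumptions.** First doses spread evenly from 1 March 2016 to 24 August 2017; PD at day 42, 84 or 168 after first dose; last dose 14 days before PD; new therapy 7 to 28 days after PD.

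**Example 1.** First dose 6 Mar 2017, scans 17 Apr and 29 May, last dose 26 Jun, PD 10 Jul, true therapy start 24 Jul.

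- Complete date: PFS event at (126 + 1)/30.4375 = 4.2 months. On-treatment ends at the earlier of 26 Jul and 23 Jul, which is 23 Jul.
- Day missing: imputed 1 Jul, before PD. PFS is censored at the 29 May scan, (84 + 1)/30.4375 = 2.8 months. On-treatment ends 30 Jun.
- Day and month missing: imputed 1 Jan 2017, before first dose. No post-baseline scan counts for BOR, PFS is censored at first dose, and on-treatment ends 31 Dec 2016, before it begins.

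**Example 2.** First dose 1 May 2017, last dose 10 Jul, PD 24 Jul, true therapy start 29 Jul. Day missing: imputed 1 Jul, nine days before the last dose. On-treatment ends 30 Jun instead of 28 Jul. PFS changes from an event at (84 + 1)/30.4375 = 2.8 months to censored at (42 + 1)/30.4375 = 1.4 months.

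**Shares over all first-dose dates, day missing.** These are shares of records with an incomplete date, not of participants.

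| Gap from PD to therapy | Imputed before PD | Imputed on or before last dose | Imputed before first dose |
|---|---|---|---|
| 7 days | 73% | 30–31% | 0% |
| 14 days | 50–51% | 8% | 0% |
| 21 days | 27–28% | 0% | 0% |
| 28 days | 5% | 0% | 0% |

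A hand check of the second column: the 1st precedes PD only if PD falls on the 2nd or later and therapy falls in the same month, so the share is about 1 − (gap + 1)/30.4375. This gives 0.74, 0.51, 0.28 and 0.05. From a gap of 30 days it is exactly zero, because the 2nd plus 30 days is always in the next month.

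**Day and month missing.** Imputed before PD in 89–99%, on or before last dose in 85–96%, and before first dose in 51–91%, depending on the gap and time to PD.

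**With a floor at last dose + 1 day.** The year-only date in Example 1 becomes 27 Jun 2017 and on-treatment ends 26 Jun. The day-missing date in Example 2 becomes 11 Jul and on-treatment ends 10 Jul. No imputed date precedes the last dose. The floor does not by itself restore the PD event: in both examples the floored date is still before PD, because the last dose was 14 days earlier.

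**The case against.** The strongest reply is that little is lost in practice.

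- **Gaps are usually long.** Protocol 5.5.1 keeps eligible subjects on treatment through the next assessment after first PD, and protocol 7.3 asks for confirmation 4 to 6 weeks later. With a gap of 28 to 42 days, a day-missing date precedes PD in 5% of affected records or none. This stands. The larger percentages concern subjects who leave without a confirmatory scan, which protocol 5.5.1 allows for, among others, therapeutic failure needing urgent therapy.
- **Year-only dates may be rare.** Further tumour therapy is asked about every 12 weeks, so the branch that precedes first dose may hardly occur. That is plausible, but the documents give no count either way.
- **BOR moves little.** A reader might infer that response rates are broadly corrupted. BOR already stops at first PD, so with the day missing the scan dropped is typically the PD scan, and a non-responder stays one. Wholesale loss of scans needs a year-only date.
- **AEs are not lost.** A reader might infer that safety data disappear. Protocol 8.5.5.1 always counts drug-related AEs after the last dose as treatment-emergent, and SAP 16.1 lists every AE. However, SAP 16.1 does not repeat the protocol rule, and that rule does not reach AEs between an imputed date and a later last dose.
- **The PFS text conflicts.** Table 3 in SAP 14.3 has no new-therapy censoring, so the PFS loss follows only from the bulleted rules.
- **Stakes are limited.** The expansion cohorts are hypothesis-generating, no tests are planned on study endpoints, and the report and addendum were delivered before this SAP version, which cancels the final analysis.

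These replies reduce the size. None supplies the missing bound.

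**Conclusion.** The point holds as a defect in a stated rule, of minor to moderate severity. Followed literally, SAP 9.8 can place post-discontinuation therapy on or before the last study dose, and before the first dose mainly when only the year is known. SAP 9.7 and 14.1 to 14.3 then carry that date into the safety window, BOR, DR and PFS.

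The effect is confined to participants with an incomplete subsequent-therapy date, whose number is not given and may be zero. The percentages rest on the assumed calendar spread, the assumed last dose 14 days before PD and the assumed gaps.

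Two stronger conclusions are tempting and not supported. One is that the reported results are materially biased: without a count of incomplete dates, the documents cannot show that. The other is that therapy sharing a month or year with PD should be dated at or after PD. Protocol 5.5.1 foresees urgent additional therapy, so therapy can truly precede documented PD. Such a rule would use the outcome to settle every doubtful case as an event.

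**What to change.** 1. Add to SAP 9.8 a separate rule for post-discontinuation anticancer drugs, radiotherapy and surgery: impute the start as the later of the existing rule date and last study-drug date + 1 day. Naming radiotherapy and surgery matters because SAP 9.7 lets them end the on-treatment period, while 9.8 covers medications only. Keep the present rule for previous and concomitant medications.
2. List every participant with an imputed subsequent-therapy date, with the recorded partial date, last dose and PD date.
3. Do not derive the therapy date from the PD date in the main analysis. Where the recorded month or year leaves their order unknown, show PFS, DR and BOR both ways as a sensitivity analysis.
4. Reconcile Table 3 with the bulleted censoring rules in SAP 14.3.

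The cost is a short paragraph, a small derivation change and a rerun of affected outputs; no new data are needed. The listing shows first whether a rerun would change anything. One limit remains: where the floor applies, the on-treatment period ends on the day of the last dose, so unrelated AEs after that day still fall outside the window.
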